2.6. STUDY PROCEDURE

Once the desired sample size is reached, a randomized controlled trial with six measurement time points will be conducted. There will be a baseline-assessment for both groups. After that, the intervention group will receive access to the online training. The introduction session and the first module can be completed directly one after the other, all further modules are always activated 4 days after the completion of the last module. The concluding session is activated at the same time as the last content-based module. The post-measurement takes place one week after completion of the last module, but no later than eight weeks after the start of the intervention. There will be an intermediate and post-assessment for both groups after the third and sixth module, respectively. The waitlist control group receives access only after the first follow-up measurement (three months after the post measurement). Two further follow-up measurements will be conducted six and twelve months after the post-assessment. The concrete chronological sequence can be seen in the following flow chart.

3. POPULATIONS OF ANALYSIS

We will conduct both an ITT analysis as well as a per protocol analysis (see also “5.1. Statistical methodology”), with the following criteria:

Inclusion criteria (included in ITT analysis):

- All valid data sets

General Exclusion criteria:

- Participants will be excluded from all analyses if
 - they do not agree with the terms of usage, usage of data and privacy policy.
 - they state that their data cannot be used in a sensible way.

Exclusion criteria PP analysis:

- Participants will be excluded from respective analyses if
 - they fill in less than 50% of questionnaires at a specific measurement point (e.g., pre-test) which address the primary outcome and secondary outcomes trained in the intervention.
 - they fill in less than 50% of a specific questionnaire.
 - they have an implausibly short time for completing the assessments (DEG_TIME in SoSci-Survey).
 - there is an abnormality in data (e.g., rating always the highest/ lowest on several scales).

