2.2. TREATMENT GROUPS

Participants will be randomly allocated to either intervention group or waitlist-control group. Stratified randomization is used, with age and gender as influencing factors. Randomization will be conducted by randomized numbers generated with Microsoft Excel. Due to the nature of the intervention, no blinding and subject replacements are planned.

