5. STATISTICAL METHODOLOGY

5.1. GENERAL METHODOLOGY

Demographics will be reported with a mean and standard deviation in continuous variables (e.g., age) and with frequency and percentage in categorical variables (e.g., sex).

Items of questionnaires will be recoded (if applicable) and a scale mean or sum score will be calculated in data processing. Mean/ Sum score and standard deviation will be reported separately by treatment group.

If applicable, mean, and standard deviation of user statistics will be calculated and reported (e.g., module completion).

T-Tests for independent samples and χ^2 -tests will be used to examine whether training groups differ in demographic data or measured variables at baseline.

HANDLING OF MISSING DATA

- On the one hand, the data will be analysed according to the "intention-to-treat" principle, with missing values being replaced using appropriate imputation procedures.
- On the other hand, the results are examined in a "per-protocol" analysis, in which only those cases are considered that have gone through the complete study protocol as predicted. We include those subjects who completed the respective content lessons (excluding the introductory and final modules) addressed in the analyses/ hypotheses. To control for influences of usage, usage of intervention will be included as a covariate in an exploratory analysis.

CLASSIFICATION OF PROTOCOL VIOLATION

Exclusion of participants due to protocol violations will be reported in the methods/ results section. To examine outliers in the questionnaire data, boxplots will be created.

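### SAP section 3 lets a participant's own statement that the data are unusable remove them from every analysis, ITT included, without saying when that statement can be made

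*SAP*

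**What the plan says.** Section 3 describes the ITT set only as the valid data sets. It does not say what makes a data set valid and does not refer to all randomised participants. Two general exclusions follow, under the lead-in "Participants will be excluded from all analyses if". The first is refusal of the terms of use, data use or privacy policy, which is a consent matter and not at issue here. The second is that "they state that their data cannot be used in a sensible way".

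The data-quality checks (under half of the questionnaires filled in, implausibly fast completion, abnormal response patterns) come under the PP criteria, with a narrower lead-in: "Participants will be excluded from respective analyses if". One of them is tied to a single measurement point.

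Elsewhere in the SAP:
- Section 2.2: "no blinding and subject replacements are planned".
- Section 2.6: "a randomized controlled trial with six measurement time points will be conducted", so five surveys follow baseline. Also: "The waitlist control group receives access only after the first follow-up measurement".
- Section 5.1: "the data will be analysed according to the 'intention-to-treat' principle", with missing values imputed. Also: "Exclusion of participants due to protocol violations will be reported in the methods/ results section".
- Section 5.2: H1-H11 use t0, t2 and t3. The later follow-ups t4 and t5 enter only H12, within the intervention group. Section 5.3 makes t1 exploratory.

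**The concern.** An ITT comparison is protected by randomisation only if staying in the set does not depend on what happens afterwards. Here a person can leave the set by their own statement. Participants know their arm, and nothing in the SAP confines the statement to the time before randomisation. If those who disown their data differ between arms in number or in outcome, the groups compared are no longer the randomised groups.

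The other safeguards do not repair this. Imputation applies to missing values of people in the analysis, not to people excluded from all analyses. The PP analysis carries the same exclusion, so agreement between ITT and PP would not be reassuring. Reporting exclusions and following CONSORT make losses visible but do not restore the comparison.

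The rule is also uneven. Someone flagged by the objective quality checks stays in ITT, while someone who doubts their own answers is removed entirely.

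**Working it through.** The SAP gives no rate of such statements, so there is no figure of its own to reproduce. The check has two parts.

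**1. Reading the rule.** The unit removed is the participant and the scope is all analyses. No survey or time window is given, and no other section limits the rule. Two things remain open: when the statement can be made, and whether it concerns one survey or all of the person's data.

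| Statement made | Consequence for ITT |
|---|---|
| Only before randomisation | No bias in the randomised comparison |
| After randomisation, about all of the person's data | Self-selected loss, possibly arm-dependent |
| After randomisation, about one survey | The same loss, and undisputed t0, t2 and t3 values go too if the survey was t1, t4 or t5 |

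**2. Possible size.** From the SAP: 120 per arm recruited, 40% dropout (so 120 × 0.6 = 72 per arm) and a planning effect of g = 0.50 (section 2.5). Assumed, because the SAP gives nothing:
- p, the share removed: 5-10% in one arm only, that is 6-12 of 120. This would arise, for example, if 1-2% disowned each of five post-baseline surveys independently: 1 − 0.99^5 = 4.9% and 1 − 0.98^5 = 9.6%.
- D, the gap between those removed and those kept on the survey driving removal: 0.5-1.0 SD.
- r, the correlation between any two surveys: .5.
- No true effect.

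*Removal depends on the t2 outcome.* The t2 mean moves by p × D and the t0 mean by r × p × D. After adjustment for t0 the shift is p × D × (1 − r²) = p × D × 0.75.
- Low end: 0.05 × 0.5 × 0.75 = 0.019 SD.
- High end: 0.10 × 1.0 × 0.75 = 0.075 SD.

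*Removal depends on another survey.* Both the t2 and t0 means move by r × p × D, so the adjusted shift is p × D × (r − r²) = p × D × 0.25, one third as large.
- Low end: 0.049 × 0.5 × 0.25 = 0.006 SD.
- High end: 0.096 × 1.0 × 0.25 = 0.024 SD.

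Simulations of 20,000 null trials per case (ANCOVA on t0, 120 per arm, Monte Carlo error about 0.001 SD for shifts and 0.002 for error rates) agree:

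| Removed, arm v arm | Gap | Removal depends on | Shift (SD) | Type I error |
|---|---|---|---|---|
| 5% v 0% | 0.5 | t2 | 0.020 | 5.2% |
| 10% v 0% | 1.0 | t2 | 0.074 | 9.9% |
| 10% v 5% | 1.0 | t2 | 0.037 | 6.3% |
| 10% v 10% | 1.0 | t2 | −0.001 | 5.0% |
| 4.9% v 0% | 0.5 | another survey | 0.005 | 4.9% |
| 9.6% v 0% | 1.0 | another survey | 0.026 | 5.6% |

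With 72 per arm, the 10% v 0% case on t2 gives the same shift (0.074) and a type I error of 7.8%. Set against g = 0.50, 0.07 SD is 0.07 / 0.50 = 14% of the planning effect, and 0.005 SD is 1%.

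**The case against.** The strongest reply is that much of this rests on silence. The SAP never links the statement to a particular survey. The wording refers to the person's data and stands next to the bullet on refusing data use, whereas the PP list names a measurement point where it means one. A reader might infer that a doubt voiced at t1, t4 or t5 certainly destroys good t2 and t3 data. The documents do not support that as fact: the person may be disowning everything, and then no undisputed data are lost. The statement might also be collected only at baseline. Both points stand, which is why the survey-specific consequence is put here only as a condition.

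A reader might also take 0.07 SD as the expected bias. It is not. It needs losses in one arm only, a full 1.0 SD gap and removal driven by the t2 outcome itself. For someone disowning a different survey, the one-third figure is the relevant one. Independent disowning over five surveys, with everyone answering all of them, also pushes the assumed share up. In the mildest cases the type I error cannot be told from 5%.

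A third reply is that the remedy helps least where the bias would be greatest. This also stands: when all declarations concern t2, a simulation of the remedy (10% removed in one arm, 1.0 SD gap) lowers the shift only from 0.073 to 0.065 SD.

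What the reply does not remove is the rule itself. It excludes the person from ITT, sets no time limit, and is qualified nowhere in the SAP.

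**Conclusion.** The point holds in a limited form. Section 3 permits exclusions from ITT on a participant's own statement, and nothing keeps that statement to the time before randomisation. If it can be made later, the rule conflicts with the intention-to-treat principle in section 5.1, and in an unblinded trial the losses may differ by arm. Whether undisputed primary-analysis data would be lost as well depends on whether the statement is survey-specific, which the SAP leaves open.

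The size is unknown and probably small: about 0.02-0.07 SD if removal acts on the t2 outcome, about 0.005-0.026 SD if it acts on another survey, and zero if both arms lose alike or the statement is made only before randomisation. The share removed, the gap, the correlation and the imbalance between arms are all assumptions. Severity is low; this is a cheap improvement, not evidence that the ITT result will be biased.

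**What to change.** Amend section 3 as follows:
- Define the ITT set as all randomised participants, analysed in the arm allocated, except those who refuse or withdraw consent to data use.
- State when the self-statement is collected and whether it concerns one survey or all of the person's data.
- Set data declared unusable after randomisation to missing (only the survey concerned, if the statement is survey-specific) and handle them under the ITT imputation.
- Apply whole-person exclusion only in the PP analysis or a sensitivity analysis.
- Report the number of such statements by arm and survey.

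This takes a few sentences and no extra data. If the disowned survey is outside the primary analysis, all t0, t2 and t3 values are kept and the shift from this source disappears. The cost is that a few poor-quality respondents stay in the denominator. Where the disowned data are t2 or t3 themselves, most of any bias at that time point remains and rests on the imputation model, which section 5.1 does not specify.

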4. OUTCOME VARIABLES

4.1. PRIMARY OUTCOME

- Resilience measured with *Stressor-Reactivity-Score* (SR-Score)

4.2. SECONDARY OUTCOMES

Related to the intervention and primary outcome

- Resilience measured with *Brief Resilience Scale* (BRS; Chmitorz et al., 2018)
- Mental Health measured with *General Health Questionnaire* (GHQ-12; Schnitz et al., 1999)
- Optimism measured with *Optimism-Pessimism-Scale* (SOP-2; Kemper et al., 2014)
- Positive reappraisal measured with subscale of *Cognitive Emotion Regulation Questionnaire* (CERQ; Loch et al., 2011)
- Acceptance measured with subscale of *Cognitive Emotion Regulation Questionnaire* (CERQ; Loch et al., 2011)
- Sense of Coherence measured with *Sense of Coherence Scale* (SOC-29; Singer et al., 2007)
- Meaning measured with subscale of *Comprehensive Inventory of Thriving* (CIT; Hausler et al., 2017)
- Self-Compassion measured with *Self-Compassion Scale Deutsch* (SCS-D; Hupfeld & Ruffieux, 2011)
- Mindfulness measured with *Mindful Attention and Awareness Scale* (MAAS-Short; Höfling et al., 2011)
- Stress measured with *Perceived Stress Scale* (PSS-2+2; Schäfer et al., in preparation)
- Stressors measured with *Mainz Inventory of Microstressors* (MIMIS; Chmitorz et al., 2020)
- Life Events measured with *Life Events Checklist-5* (LEC-5; Krüger-Gottschalk et al., 2017)
- Anxiety/ Depression measured with *Generalized Anxiety Disorder-7* (GAD-7) and *Patient Health Questionnaire-9* (PHQ-9; Löwe et al., 2002)

Further (exploratory) outcomes

- Positive (Re-)appraisal measured with *Positive Appraisal Style Scale Content* (PASS-content) and *Positive Appraisal Style Scale Process* (PASS-process; Petri-Romao et al., 2021)
- Social Support measured with *Osloer Social Support Scale* (OSS-3; Kocalevent et al., 2018)
- Control beliefs with *Internal-External Locus of Control Short Scale-4* (IE-4; Kovaleva et al., 2014)
- Self-Efficacy measured with *German Version of Self-Efficacy Short Scale* (Allgemeine Selbstwirksamkeit Kurzsкала, ASKU; Beierlein et al., 2014)
- Coping measured with *Coping Orientation to Problems Experienced Inventory* (Brief-COPE; Knoll et al., 2005)
- Self-Esteem measured with *German Single-Item Self-Esteem Scale* (G-SISE; Brailovskaia & Margraf, 2020)
- Positive Affect measured with subscale of *Positive and Negative Affect Schedule* (PANAS; Breyer & Bluemke, 2016)
- Life Satisfaction measured with *Satisfaction with Life Scale* (SWLS; Janke & Glöckner-Rist, 2012)
- Well-Being measured with *WHO-5 Well-Being Index* (Brähler et al., 2007)
- Functionality measured with *World Health Organization Disability Assessment Schedule* (WHODAS 2.0; Üstün et al., 2010)
- Coping Flexibility measured with *Coping Flexibility Questionnaire Revised* (CFQ-R; Kato, 2012)

- Satisfaction with Intervention measured with *Client Satisfaction Questionnaire-Intervention* (CSQ-I; Boß et al., 2016)
- Adverse Effects measured with *Inventory for the Assessment of Negative Effects of Psychotherapy* (INEP; Ladwig et al., 2014)
- Relationship to Intervention measured with *Mobile Agnew Relationship Measure* (mARM; von Wulffen et al., 2022)
- Self-Care measured with *Hamburger Selbstfürsorgefragebogen* (Hamburg Self-Care Survey; Harfst et al., 2009)
- Mental Health Literacy measured with *Mental Health Literacy Questionnaire* (MHLQ; Dias et al., 2018), *Mental Health Literacy Scale* (MHLS; O'Connor & Casey, 2015), *Mental Health Knowledge Schedule* (MAKS; Evans-Lacko et al., 2010), *Health Literacy Survey EU 16* (HLS EU 16; Jordan & Hoebel, 2015), *eHealth Literacy Scale* (eHEALS; Soellner et al., 2014), *Well-being Literacy Scale* (Hou et al., 2021), *STRESS K-10* (Giesinger et al., 2008), *Fragebogen zur Erhebung des Wissens über psychosoziale Versorgungsstrukturen* (Questionnaire to survey knowledge of psychosocial care structures; Fritz, 2021)
- Belief Towards Mental Illness Scale (Hirai & Clum, 2018)
- Help-seeking behaviour measured with *General Help Seeking Scale* (GHSS; Rickwood et al., 2005) and *Attitudes Toward Seeking Professional Psychological Help* (ATSPPH; Kessler et al., 2015)

4.3. OTHER PARAMETERS

DEMOGRAPHY AND BASELINE

Demographic measures:

- Age
- Sex
- Educational background/ status
- Number of persons living in the household
- Household net income
- Individual net income

Baseline variables

- Attitudes towards psychological online interventions measured with *Attitudes towards Psychological Online Interventions Questionnaire* (APOI; Schröder et al., 2015)
- Personality measured with *Big Five Inventory-10* (BFI-10; Rammstedt et al., 2017)

USER STATISTICS

Intervention

- Number of processed modules
- Processing time of the individual contents as well as of the entire intervention
- Contents from the feedback questionnaire (e.g., how well the last module was liked)
- Stress and resilience history/ state queries
- Days of usage

Survey

- Response times, namely
 - Per questionnaire (how long the user spent on each questionnaire)
 - Total processing time for all questionnaires (after adjustment for interruptions)
- Percentage of missing answers in the questionnaires (absolute and relative to total length of the survey)
- "DEG_TIME" as normalized indicator for extremely fast completion of questionnaires

4.4. Hypotheses

1. The intervention will significantly increase resilience, measured with the SR Score, in the intervention group (IG) compared with a waitlist control (WLC) group at t_2 and t_3 compared to t_0 .
2. The intervention will significantly increase resilience, measured with the Brief Resilience Scale, in the intervention group (IG) compared with a waitlist control (WLC) group at t_2 and t_3 compared to t_0 .
3. The intervention will significantly reduce the perceived stress in the intervention group (IG) compared with a waitlist control (WLC) group at t_2 and t_3 compared to t_0 .
4. The intervention will significantly increase the optimism in the intervention group (IG) compared with a waitlist control (WLC) group at t_2 and t_3 compared to t_0 .
5. The intervention will significantly increase the mindfulness in the intervention group (IG) compared with a waitlist control (WLC) group at t_2 and t_3 compared to t_0 .
6. The intervention will significantly increase the meaningfulness in the intervention group (IG) compared with a waitlist control (WLC) group at t_2 and t_3 compared to t_0 .
7. The intervention will significantly increase the acceptance in the intervention group (IG) compared with a waitlist control (WLC) group at t_2 and t_3 compared to t_0 .
8. The intervention will significantly increase the self-compassion in the intervention group (IG) compared with a waitlist control (WLC) group at t_2 and t_3 compared to t_0 .
9. The intervention will significantly increase the mental health in the intervention group (IG) compared with a waitlist control (WLC) group at t_2 and t_3 compared to t_0 .
10. The intervention will significantly reduce depressive symptoms in the intervention group (IG) compared with a waitlist control (WLC) group at t_2 and t_3 compared to t_0 .
11. The intervention will significantly reduce anxiety in the intervention group (IG) compared with a waitlist control (WLC) group at t_2 and t_3 compared to t_0 .
12. In the intervention group, the intervention will lead to improved resilience by the end of the intervention (at t_2) and these improvements should be maintained at the respective follow-ups (at t_3 , t_4 , t_5 ; probably to a lesser degree).

Further longitudinal effects, intervention effects at intermediate measurements (t_1), other resilience-related outcomes, moderator and mediator analyses will be examined exploratorily. Therefore, no specific hypotheses are stated.

5. STATISTICAL METHODOLOGY

5.1. GENERAL METHODOLOGY

Demographics will be reported with a mean and standard deviation in continuous variables (e.g., age) and with frequency and percentage in categorical variables (e.g., sex).

Items of questionnaires will be recoded (if applicable) and a scale mean or sum score will be calculated in data processing. Mean/ Sum score and standard deviation will be reported separately by treatment group.

If applicable, mean, and standard deviation of user statistics will be calculated and reported (e.g., module completion).

T-Tests for independent samples and χ^2 -tests will be used to examine whether training groups differ in demographic data or measured variables at baseline.

HANDLING OF MISSING DATA

- On the one hand, the data will be analysed according to the "intention-to-treat" principle, with missing values being replaced using appropriate imputation procedures.
- On the other hand, the results are examined in a "per-protocol" analysis, in which only those cases are considered that have gone through the complete study protocol as predicted. We include those subjects who completed the respective content lessons (excluding the introductory and final modules) addressed in the analyses/ hypotheses. To control for influences of usage, usage of intervention will be included as a covariate in an exploratory analysis.

CLASSIFICATION OF PROTOCOL VIOLATION

Exclusion of participants due to protocol violations will be reported in the methods/ results section. To examine outliers in the questionnaire data, boxplots will be created.

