2.1. STUDY DESIGN

This intervention study uses a waitlist control design with two arms. 240 adults – 120 in intervention group (IG) and 120 in waitlist-control group (CG) – participate in a randomized controlled trial. Whereas the IG immediately gains access to the 6-week resilience intervention "resiLIR Basic" after the baseline measurement the CG is only enabled to participate in the online intervention after the first follow-up assessment. Further details are specified in the study procedure (2.6.). The online intervention "resiLIR Basic" consists of 8 modules of about 45-60 minutes length using psycho-educational elements and practical exercises to address evidence-based resilience factors, such as optimism or sense of coherence. Participants will complete online surveys on resilience, mental health, and several resilience factors pre-, during and post-intervention as well as 3, 6 and 12 months after completion as follow-up assessments. The main question is whether the intervention is effective in increasing psychological resilience.

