- Self-compassion (7): In the lesson on self-compassion, users learn what self-compassion is, how it differs from self-esteem, and what the effects of self-compassion are. In addition, the users learn how self-compassion can be trained and how it can be used to strengthen resilience.

- Conclusion (8): In the last lesson of the training program, users reflect on what they have learned. They plan the future implementation of some strategies in everyday life and identify their own early warning signals for stress. Finally, there is an exercise to appreciate the small and large successes.

All lessons are approximately 45-60 minutes in length each. Various additional materials are also provided for each lesson. This includes, for example, literature and media recommendations or further exercises to deepen the content already learned.

[figure not shown]
The individuals in the waiting control group initially receive no intervention. As soon as the participants have completed the first follow-up, the intervention is also activated for the control group.

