2.5. SAMPLE SIZE

Previous studies from our research groups have shown a medium to large effect size for the stressor reactivity score as a primary outcome measure in online intervention studies for resilience (AG [name], unpublished). Because a large effect size was found only in a particularly stressed population, which is not expected in the sample addressed here, we assume a medium effect here (Hedges' $g = .50$). Therefore, the sample size design was calculated with a medium effect size, a significance level of 0.05 and a power of 0.90 using G*Power (Faul et al., 2007). This results in a required sample size of $n = 74$ per group ($N = 146$). As there are high dropout rates for online interventions (van Ballegooijen et al., 2014) we decided to recruit $n = 120$ individuals per group. This number is based on an assumed dropout rate of 40%.

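### For H1–H11 the per-protocol rule selects on lesson completion in the intervention arm only, and the SAP does not say that ITT decides

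*SAP*

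**What the plan says.** Section 5.1 (Handling of missing data) plans two analyses side by side: intention-to-treat with imputation, and per-protocol. For the second, "We include those subjects who completed the respective content lessons (excluding the introductory and final modules) addressed in the analyses/ hypotheses". Usage is to be a covariate, in an exploratory analysis only. Section 3 adds per-protocol exclusions on questionnaire completeness, implausibly fast completion and abnormal response patterns. These are not tied to one arm.

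On controls, section 2.4 says "The individuals in the waiting control group initially receive no intervention", and section 2.6 says "The waitlist control group receives access only after the first follow-up measurement". Section 5.2 identifies the first follow-up as t3 and compares the arms over t0, t2 and t3 for H1–H11, with the t0 value as covariate. No section gives a lesson-based rule for controls, says whether ITT or per-protocol decides a hypothesis, or plans a randomisation-based estimate of the effect in completers.

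**The concern.** Completing lessons is behaviour after randomisation, and up to t3 it can be seen in one arm only. Read literally, the rule leaves no controls in the per-protocol set for H1–H11. Read sensibly, it compares intervention participants who kept going with all controls who pass the data-quality rules, including those who would have stopped. The controls who would have completed cannot be identified, so rewording the control-side rule does not restore the balance.

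The planned adjustments do not close the gap:

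- The t0 covariate removes only the part of the completer/non-completer difference that t0 predicts.
- Usage is itself post-randomisation and is zero for every control up to t3, so it cannot separate motivation from training.
- Attitudes to online interventions and personality are measured at baseline, but are named only as exploratory moderators or mediators.

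At stake is how the results are read. If per-protocol exceeds ITT, the difference may reflect dilution of ITT by non-completers, selection, or both, and the planned analyses cannot tell these apart.

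**Working it through.** **The plan's own figures.** The SAP gives no figure for the completer effect. The inputs it does give are the allocation ("120 in intervention group (IG) and 120 in waitlist-control group (CG"), an effect of g = .50, and "This number is based on an assumed dropout rate of 40" per cent. Then 120 × 0.60 = 72 per group, close to the stated requirement of 74.

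**Assumptions, not in the SAP.** The completer share is π = .60, which borrows the dropout rate as the rate of lesson non-completion. δ is the difference in outcome, in SD and beyond t0, between completers and non-completers if neither were trained. The t0–t2 correlation is .5. All controls are retained.

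**Size of the bias.** Untreated completers average δ above non-completers. Controls, a mixture of both types, average πδ. With no training effect the per-protocol contrast is therefore δ − πδ = (1 − π)δ.

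| π | δ = .2 | δ = .3 | δ = .5 |
|---|---|---|---|
| .5 | .10 | .15 | .25 |
| .6 | .08 | .12 | .20 |
| .7 | .06 | .09 | .15 |

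**False positives.** The residual SD after t0 adjustment is √(1 − .5²) = .87. SE = .87 × √(1/72 + 1/120) = .13. At δ = .3 the standardised shift is .12/.13 ≈ .93, which gives about 15% two-sided rejection. Simulated ANCOVAs (6,000 trials per setting) gave 9.5%, 15% and 32% for δ = .2, .3 and .5. With SD 1 in place of .87, the rates were 8.3%, 11.8% and 25.2%.

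**With a true completer effect of .50** and no benefit in non-completers, at δ = .3:

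- Per-protocol: .50 + .12 = .62.
- ITT: .60 × .50 = .30.
- ITT/π: .30/.60 = .50.

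Simulated two-stage regression, with allocated arm as instrument and binary completion as exposure, gave .50 here. With no effect it gave 0, with about 5% rejection. Its SD was .19 against .13 for the completer comparison (by hand: .87 × √(2/120)/.60 = .19).

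**Where these figures move.**

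- *Controls also selected by the questionnaire exclusions.* Suppose 90% of would-be completers and 40% of the others are retained. The would-be-completer share among retained controls is .54/(.54 + .16) = .77, and the bias at δ = .3 is (1 − .77) × .3 = .07.
- *Few non-completers answer t2.* If 20% do and only complete cases are used, the completer share among intervention participants seen is .60/.68 = .88. With no effect, the instrumental estimate is (.88 − .60) × .3/.88 ≈ .10. For a true .50 it is about .60.
- *Partial benefit.* If non-completers keep 30% of the benefit, binary completion gives (.30 + .40 × .15)/.60 = .60.
- *Lesson count as exposure.* If non-completers average 3 of 6 lessons with no benefit, mean exposure is .60 × 6 + .40 × 3 = 4.8, and 6 × .30/4.8 = .375 for a true .50. If they average 1 lesson with 60% of the benefit, it is 6 × (.30 + .40 × .30)/(3.6 + .4) = .63.

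**The case against.** The strongest reply is that ITT is planned, is listed first, and protects the randomised comparison. Per-protocol is a common companion analysis, and the SAP never calls it the effect of the full course. With one instrument, the two-stage model tests essentially the same null hypothesis as ITT. This stands, and it confines the point to the per-protocol result. It does not remove the point, because section 5.1 puts the two analyses side by side with no order of priority.

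Four stronger readings are tempting, and the SAP does not support them:

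- *Every per-protocol participant must finish all six content lessons.* Section 5.1 refers to the lessons relevant to the hypothesis. Optimism (H4) would plausibly need lesson 3 and mindfulness (H5) lesson 4. One completer share for H1–H11 is therefore an assumption, and selection is probably weaker for single early lessons.
- *Controls are wholly unselected.* They are unselected on lessons, but the section 3 exclusions apply to them too. If those exclusions mirrored lesson completion exactly, the bias would vanish. Nothing in the SAP makes that likely or checkable.
- *A per-protocol result larger than ITT would prove bias.* Dilution alone gives .30 against an unbiased .50 at 60% completion. The upward direction also needs completers to do better untreated, which no section states.
- *Randomisation delivers an unbiased completer effect.* It removes self-selection only if allocation acts through the lessons alone and non-completers' outcomes are observed or credibly imputed. A lesson count does not escape this, since it needs benefit to be linear in lessons.

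**Conclusion.** The point holds in a limited form. For H1–H11 the per-protocol rule conditions on post-randomisation behaviour that can occur in one arm only, and neither the t0 covariate nor the usage covariate corrects this. With 60% completers and a gap of .2 to .5 SD the bias is .08 to .20 SD, which is 16% to 40% of the assumed g = .50 (.08/.50 and .20/.50). These sizes rest on the assumed gap, on the dropout rate standing in for non-completion, and on full retention of controls, so they lie towards the unfavourable end. The direction is upward only if completers would fare better without training.

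A reader might infer that the trial's main comparison is compromised. It is not, since ITT is planned. The change should be made before the data are seen, because the SAP gives the two analyses no order of priority.

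**What to change.** 1. In sections 5.1 and 5.2, state that the ITT comparison decides H1–H11 and that the lesson-completer comparison is descriptive and non-randomised.
2. Add a supplementary completer estimate for H1–H11: two-stage regression on all randomised participants, with allocated arm as instrument, completion of the respective lessons before the survey as exposure and the t0 value as covariate, on the same imputed data as ITT.
3. Add a sensitivity analysis with the number of content lessons completed as exposure, because partial users may benefit.
4. State the assumptions: allocation acts only through the lessons (for the count version, linear benefit per lesson), and non-completers' outcomes are observed or credibly imputed. Show how the estimate moves when these fail.

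The cost is SAP wording and one extra model per outcome, plus its sensitivity version. No new data are needed, since section 4.3 already lists the number of modules processed. The price is a wider interval (SD about .19 against .13) and dependence on the imputation, which section 5.1 does not yet specify.
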